**Original Release: 15 July 2013**

**Current Version: 03 October 2014**

## 2. Protocol Synopsis

EWOLUTION - REgistry on WATCHMAN Outcomes in Real-Life Utilization	
Objective(s)	
 
• To compile real-world clinical outcomes data for WATCHMAN LAA (Left Atrial Appendage) Closure Technology in patients who are implanted with the WATCHMAN device in a commercial clinical setting.
 
• To collect real-world usage data that may be needed for reimbursement of WATCHMAN technology in certain countries.
 

Marketing Performance Expectation	The WATCHMAN LAA Closure Technology is designed to prevent embolization of thrombi that may form in the LAA, thereby preventing the occurrence of ischemic stroke and systemic thromboembolism.
Test Device	WATCHMAN LAA Closure Technology
Device Sizes	21mm, 24mm, 27mm, 30mm, 33mm
Study Design	This is an observational, prospective, non-randomized, multicenter study.
Planned Number of Subjects	Approximately 1000 subjects will be enrolled in the study.
Planned Nr of Centers/Countries	Up to 70 sites in the International (Outside of US) region.
Primary Endpoint	Primary analyses may include, but will not be limited to, the following: procedural complications, incidence of stroke and death. Descriptive statistics will be used for baseline, procedure and follow-up data collected through the study.
Study Duration	Enrolment is expected to be completed in 21 months; therefore the total study duration is estimated to be 48 months.
Follow-up (FU) Schedule	
Each patient will be followed for a period of two years after enrolment according to the schedule and standard practice at the enrolling centers. There will be no additional visits, nor procedures, for subjects who participate in the study. Subjects are expected to be followed at implant, then at one post-implant visit (typically between 1-3 months of implant), and then annually through 2 years post implant. An intermediate visit may be a scheduled in a number of patients, per physician discretion. In order to reliably capture patient status at study end a FU window of <math>24 \pm 3</math> months will be considered acceptable for scheduling the last visit.
 
For subjects who are not scheduled to visit the clinic for a follow-up, a subject contact (e.g. phone call) will ensure capture of the endpoint related information, however it is recommended to perform an in-office visit for at least the first annual visit.

EWOLUTION - Registry on WATCHMAN Outcomes in Real-Life Utilization						
	Data Collection Overview					
	Data Collected	BASELINE	IMPLANT	Follow Up		
				Post-implant Visit*	FU office visit	FU phone visit
	Informed Consent	X				
	Inclusion/Exclusion	X				
	Demographic data	X				
	Medical History	X				
	LAA imaging (e.g. TEE)		X	X §	X **	
	Medication Regimen	X	X	X	X	X
	Current status and Vital Signs	X	X	X	X	
Adverse Event Reporting	X	X	X	X	X	

*expected 1-3 month from implant depending on center's practice  § Control TEE/CT is clinical standard after the Watchman procedure to ensure sealing and exclude thrombus on the device prior to stop dual platelet inhibition or warfarin  ** collected only if performed, according to center's practice
						
Key Inclusion Criteria	
A subject may be enrolled in the study if all of the following inclusion criteria are met, provided no exclusion criteria are met:
 
 
1. Patients who are eligible for a WATCHMAN device according to current international and local guidelines (and future revisions) and per physician discretion;
 
2. Patients who are willing and capable of providing informed consent, participating in all testing associated with this clinical investigation at an approved clinical investigational center;
 
3. Patients whose age is 18 years or above, or of legal age to give informed consent specific to state and national law.
 
					
Key Exclusion Criteria	
Subjects will be excluded from the study if they meet any of the following criteria:
 
 
1. Patients who are currently enrolled in another investigational study or registry that would directly interfere with the current study, except when the patient is participating in a mandatory governmental registry, or a purely observational registry with no associated treatments. Each instance should be brought to the attention of the sponsor to determine eligibility.
 
2. Women of childbearing potential who are, or plan to become, pregnant during the time of the study (method of assessment upon physician's discretion);
 
					

EWOLUTION - REgistry on WATCHMAN Outcomes in Real-Life Utilization									
	3. The subject is unable or not willing to complete follow-up visits and examination for the duration of the study.								
Statistical Methods									
Statistical Test Method	No formal pre-specified hypotheses will be tested. However, a variety of statistical modeling methods may be utilized in order to assess associations between the likelihood of each of the three outcomes and the pre-specified patient and procedural characteristics, including multivariate logistic regression and classification and regression tree models.								
Sample Size Parameters	
This is a prospective, multicenter non-randomized observational study with no formal pre-specified hypothesis test. All subjects will be followed for up to 2 years or until the study is terminated.
 
A sample size of up to 1000 subjects was chosen to assess incidence of rare events with a large degree of precision. The table below provides the two-sided 95% confidence interval assuming an event rate of 5%.
 
Two-Sided Confidence Interval by Sample Size:
 
  
 Sample Size	95% CI	
   
 500	5% ± 1.9%	
 
 750	5% ± 1.6%	
 
 1000	5% ± 1.4%	
  
	Sample Size	95% CI	500	5% ± 1.9%	750	5% ± 1.6%	1000	5% ± 1.4%
Sample Size	95% CI								
500	5% ± 1.9%								
750	5% ± 1.6%								
1000	5% ± 1.4%								

## 4. Introduction

### i) Background

Atrial fibrillation (AF) is one of the most common abnormal rhythm disturbances and affects approximately 5.5 million people worldwide, including 10% of people older than 75 years. The most debilitating consequence of AF is thrombus formation from stagnant blood flow leading to thromboembolism and stroke. As such, the rate of ischemic stroke attributed to non-valvular AF is estimated to average 5% per year which is 2-7 times that of those without AF.

Treatment with warfarin therapy for the prevention of thromboemboli originating in the left atrial appendage has been well documented. Warfarin therapy targeting an International Normalized Ratio (INR) between 2.0 – 3.0 is considered the gold standard treatment today for patients with non-valvular AF for prevention of stroke. While warfarin has remained the optimum treatment for many years, there are numerous challenges with the drug, such as frequent need for monitoring and dosage adjustments, dietary and metabolic interactions, and concerns of patient compliance. Additionally, the potential for frequent and fatal bleeding are high concerns for patients and caregivers and often it is found this drug is not well tolerated.

Currently available alternatives to warfarin are the new oral anticoagulants (NOACs) which include dabigatran, rivaroxaban, apixaban. Unlike Warfarin, NOACs can be administered without the need for monitoring, have fewer food and drug interactions and provide an improved efficacy/safety ratio. Dabigatran at the dose of 150 mg twice daily is shown to be superior to warfarin in prevention of stroke and systemic thromboembolism, has a favorable safety profile including significantly less intracranial bleeding and comparable extracranial bleeding, and is associated with less cardiovascular mortality. Rivaroxaban at a daily dose of 20 mg is shown to be noninferior to warfarin in prevention of stroke or systemic embolism. The risk of major bleeding is not significantly different for rivaroxaban vs warfarin, however, intracranial and fatal bleeding is less frequent with rivaroxaban. In comparison to warfarin, apixaban at a dose of 5 mg twice daily is also shown to be superior in prevention of stroke and systemic thromboembolism, causes less bleeding, and is associated with a lower mortality rate.

As the risk of stroke increases with age and the disability and tolerance concerns with available drug therapy persist, the need for permanent protection against thromboembolism in AF patients remains unmet. The sponsor has developed the WATCHMAN® Left Atrial Appendage Closure (LAA) Device, a permanent implantable device to seal off the left atrial appendage, the location where the vast majority of thrombi originate in AF patients. This device may provide an alternative to warfarin therapy in non-valvular AF patients who require thromboembolic protection. The current study is designed to compile real-world clinical outcomes data for WATCHMAN LAA Closure Technology in subjects with non-valvular AF.

### ii) WATCHMAN Therapy

The WATCHMAN® LAA Closure Technology is intended for patients with non-valvular atrial fibrillation who require treatment for potential thrombus formation.

The implanted component of the system, hereafter referred to as the WATCHMAN device, is an approved commercially available novel device designed to prevent the embolization of thrombi that may form in the LAA. The WATCHMAN device may prevent the occurrence of ischemic stroke and systemic thromboembolism in patients with non-valvular AF who require treatment for potential thrombus formation. It may also reduce the risk of life-threatening bleeding events such as hemorrhagic stroke by potentially removing the need for anticoagulation therapy. The WATCHMAN device is manufactured by Boston Scientific, received CE Mark in October 2005, and is under IDE in the United States (U.S.).

### iii) WATCHMAN Clinical Study Experience

Clinical evaluation of the WATCHMAN LAA Closure Technology has been ongoing since 2002, with all U.S. studies conducted under IDE #G020312. **Table 1** lists the clinical studies conducted with the WATCHMAN device.

**Table 1: Clinical Studies of the WATCHMAN Device**

Study	Dates of Enrolment	Enrolled Subjects	Sites	Follow-Up
Pilot (feasibility study)	Aug 2002 – Jan 2005	66	8	U.S. subjects completed 5 years; OUS subjects completed up to 9 years.
PROTECT AF (pivotal study)	Feb 2005 – Jun 2008	800	59	Ongoing through 5 years
CAP Registry	Aug 2008 – Jun 2010	566	26	Ongoing through 5 years
ASAP (feasibility study)	Jan 2009 – Nov 2011	150	4	Ongoing through 2 years
PREVAIL (pivotal study)	Nov 2010 – Jun 2012	461	41	Ongoing through 5 years
CAP2 Registry	Sep 2012 - ongoing	Up to 1500	Up to 60	Ongoing through 5 years

The first pilot study demonstrated that the WATCHMAN device was safe and met the performance criteria for use in subjects with non-valvular atrial fibrillation.

The first pivotal study, WATCHMAN Left Atrial Appendage System for Embolic PROTECTION in Patients with Atrial Fibrillation (PROTECT-AF), demonstrated non-

inferiority of the WATCHMAN device to long-term warfarin therapy for the primary efficacy endpoint of stroke, systemic embolism and cardiovascular death.

Most recent data analysis of The PROTECT AF trial has shown that the WATCHMAN device achieved superiority for the combined endpoint of all stroke, cardiovascular or unexplained death and systemic embolism (for Bayesian analysis, posterior probabilities are used to determine superiority; > 95% represents superiority).

- The observed primary efficacy event rate was 2.3 percent and 3.8 percent in the WATCHMAN and control groups, respectively, demonstrating a 40 percent relative risk (RR) reduction in primary efficacy in the WATCHMAN group (RR = 0.60, posterior probability of superiority = 96 percent).

Secondary analysis also showed a relative risk reduction and superiority to control for all-cause mortality and cardiovascular mortality.

- All-Cause Mortality: the WATCHMAN group was superior to the control group, 3.2 percent to 4.8 percent respectively, representing a 34 percent relative risk reduction in all-cause mortality in the WATCHMAN group (Hazard ratios [HR] = 0.66, p=0.0379).
- Cardiovascular Mortality: the WATCHMAN group was superior to the control group, 1.0 percent and 2.4 percent respectively, representing a 60 percent relative risk reduction in cardiovascular death in the WATCHMAN group (HR = 0.40, p=0.0045).

The Continued Access to PROTECT Registry (CAP Registry) provided continued access of the WATCHMAN device to PROTECT-AF investigators and demonstrated a decrease in procedural complications of pericardial effusion with tamponade, cardiac perforation and device embolization (1.2%, 0.2%, 0%, respectively).

The second pivotal study, Prospective Randomized Evaluation of the WATCHMAN LAA Closure Device In Patients with Atrial Fibrillation Versus Long Term Warfarin Therapy (PREVAIL), was conducted to provide additional information on the implant procedure and complication rates associated with the device.

The ASA Plavix Feasibility Study With WATCHMAN Left Atrial Appendage Closure Technology (ASAP) study was a feasibility study conducted in Europe to characterize the performance of the WATCHMAN device in non-valvular atrial fibrillation (AF) subjects with contraindications to warfarin therapy.

The Continued Access Protocol (CAP2) is a prospective, non-randomized, multicenter study to allow continued access to the WATCHMAN LAA Closure Technology during the data analysis, reporting and review of the PREVAIL pivotal study Pre-Market Application by FDA.

## 5. Device Description

The WATCHMAN device is designed to be permanently implanted at or slightly distal to the ostium (opening) of the LAA to prevent embolization of blood clots formed within the trabeculated LAA. The placement procedure can be performed under general or

[figure not shown]
conscious sedation in a catheterization or electrophysiology (EP) laboratory setting using standard transseptal technique under fluoroscopic and echocardiographic guidance.

The WATCHMAN LAA Closure Technology is a three-component system which includes the WATCHMAN LAA Closure Device (WATCHMAN device), the WATCHMAN Delivery System and the WATCHMAN Access Sheath.

#### i) WATCHMAN Device

The WATCHMAN device is comprised of a self-expanding nitinol frame structure with fixation anchors around the device perimeter and a permeable polyester fabric that covers the atrial facing surface of the device (*Figure 1*). The device is constrained within the Delivery System until deployment into the LAA. The WATCHMAN device is available in various sizes to accommodate a range of LAA ostial diameters. The device size, measured in mm, is the diameter of the device at its maximum dimension in an uncompressed (fully expanded) state. An appropriate device size is selected based on LAA measurements obtained utilizing Fluoroscopy and Transesophageal Echocardiography (TEE).

*Figure 1: WATCHMAN Device*

#### ii) WATCHMAN Delivery System

The delivery catheter consists of an inner core wire with a reinforced braided jacket that is connected to the deployment knob at the proximal end and a screw thread assembly at the distal end. The outer sheath has an overall profile of 12 French.

The WATCHMAN device is pre-loaded and is deployed by loosening the valve on the Delivery System and retracting the outer sheath. The WATCHMAN device can be partially recaptured and redeployed if the device is too distal. If the device is deployed too proximal, it can be fully recaptured. The device is released by rotating the device deployment knob counter clockwise.

### iii) WATCHMAN Access Sheath

The 14 French transseptal Access Sheath is utilized to gain access to the LAA and serves as a conduit for the Delivery System. The distal end of the Access Sheath is available in various curve styles to assist with placement of the sheath into the LAA. Various curve styles allow for coaxial placement of the sheath into the LAA. The distal tip contains a marker band for in situ visualization as well as sizing marker bands used to gauge if the Access Sheath is positioned at the appropriate depth in the LAA based on the device size selected.

The Access Sheath and dilator are utilized to gain access to the LAA after initial transseptal access into the left atrium has been established. Once the Access Sheath is positioned into the left atrium and the dilator has been removed, it then serves as a conduit for the Delivery System. The Delivery System is introduced into the Access Sheath and the components snap together to act as one during device implantation.

## 6. Objectives

The objective of the study is to compile real world clinical data on the use of the WATCHMAN LAA Closure Technology in a commercial clinical setting.

The study aims to obtain additional clinical data on procedural success and complications, as well as information about long-term patient outcomes, including clinical data on incidence of stroke/TIA.

The collected real-world data may be needed for reimbursement of WATCHMAN technology in certain countries.

## 7. Endpoint Analysis

Primary analyses may include, but will not be limited to, the following: procedural complications, incidence of stroke and death. Descriptive statistics will be used for baseline, procedure and follow-up data collected through the study.

## 8. Design

This WATCHMAN Registry is an observational, prospective, non-randomized, multicenter study.

### 8.1. Scale and Duration

Approximately 1000 subjects will be enrolled at up to 70 sites in the International (Outside the US) region.

Each patient will be followed for a period of two years after implant according to the schedule. There will be no additional visits for subjects who participate in the study.

It is anticipated that enrolment will be conducted over a period of 21 months; therefore the total study duration is estimated to be 48 months.

## **8.2. *Justification for the Study Design***

This is a purely observational post-market data collection designed to compile real-world clinical outcomes data for WATCHMAN LAA Closure Technology. The implant of the device is done according to the patient clinical indications, regardless of participation in the study. The post-implant TEE (or alternative imaging methods) is also a clinical standard after the Watchman procedure to ensure sealing and exclude thrombus on the device prior to stop dual platelet inhibition or warfarin. The patients are followed per standard of care (no additional burden for the patient like additional invasive examination or additional follow-up).

## **9. Subject Selection**

### **9.1. *Study Population and Eligibility***

Any patient, who meets all the inclusion criteria, does not meet any of the exclusion criteria, and who provides written informed consent may be enrolled in the study. The subjects selected for participation will be from the investigator's general patient population. The investigator has the responsibility for screening all potential patients and selecting those who meet study inclusion/exclusion criteria as described in sections 9.2 and 9.3.

### **9.2. *Inclusion Criteria***

A subject may be enrolled in the study if all of the following inclusion criteria are met, provided no exclusion criteria (see section 9.3) are met:

1. Patients who are eligible for a WATCHMAN device according to current international and local guidelines (and future revisions) and per physician discretion;
2. Patients who are willing and capable of providing informed consent, participating in all testing associated with this clinical investigation at an approved clinical investigational center;
3. Patients whose age is 18 years or above, or of legal age to give informed consent specific to state and national law.

### **9.3. *Exclusion Criteria***

Subjects will be excluded from the study if they meet any of the following criteria:

1. Patients who are currently enrolled in another investigational study or registry that would directly interfere with the current study, except when the patient is participating in a mandatory governmental registry, or a purely observational registry with no associated treatments. Each instance should be brought to the attention of the sponsor to determine eligibility.

2. Women of childbearing potential who are, or plan to become, pregnant during the time of the study (method of assessment upon physician's discretion);
3. The subject is unable or not willing to complete follow-up visits and examination for the duration of the study.

## **10. Subject Accountability**

### **10.1. Enrolment**

Subjects who meet the eligibility criteria as per 9.2 and 9.3, have signed and dated the Informed Consent Form and actually undergo a WATCHMAN implant procedure are considered enrolled in the study. Baseline data from subjects who meet the eligibility criteria as per 9.2 and 9.3, have signed and dated the Informed Consent Form but do not eventually undergo a WATCHMAN implant procedure are collected for epidemiological reasons, to better characterize the population. The start of the WATCHMAN implant procedure is considered the insertion of the WATCHMAN Access Sheath.

### **10.2. Withdrawal**

Every effort should be made to retain subject enrolment for the duration of the study. During the informed consent process subjects should be fully informed of the data collection requirements and duration, and should only be enrolled if willing to fully participate in it. All subjects enrolled in the clinical study must be accounted for and documented. Reasons for withdrawal may include physician discretion, subject choice to retire consent, loss to follow-up, or death. In the event a subject does decide to withdraw from the study, every effort should be made to obtain full information on any on-going adverse events.

Subjects should only be considered lost to follow-up after significant effort has been made to contact the subject. At a minimum there should be 3 documented telephone contact attempts and one certified letter sent to the subject's last known residence. Subject withdrawal and lost to follow-up will be documented on the "End of Study" CRF. For subjects who are "lost-to-follow-up" the investigator/center should make documented attempts to contact the subject prior to completion of the applicable CRF. Additional data may no longer be collected after the point at which a subject has been withdrawn from the study or withdraws his/her consent, for whatever reason. All open adverse events should be closed or documented as chronic. Data collected up to the point of subject withdrawal may be used, unless any local regulations apply which require removal of the data.

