### 12.2. Statistical Analysis

Analysis will include all subjects enrolled into the study who undergo an attempted implant of the WATCHMAN device. While no formal hypothesis tests will be performed, descriptive statistics will be generated for the data collected at baseline, during the implant procedure and at follow-up. For continuous variables, the mean, standard deviation, median, range and 95% confidence intervals will be reported. Confidence intervals (95%) for the difference between means will be used to compare groups. For proportions, 95% confidence intervals will be reported. For time-to-event analyses, all subjects not having an event or lost to follow-up will be censored at the time of the last documented follow-up visit. Analyses may include, but will not be limited to, the following: procedural success, procedural complications, and incidence stroke/TIA.

A variety of methods may be utilized in order to assess associations between the likelihood of each of the three outcomes and the patient and procedural characteristics outlined below. Covariates will be chosen for inclusion in the models based on the number of patients with complete data for each outcome according to the prioritization in Table 4: Covariates of Interest.

Methods to model multivariate associations may include but are not limited to the following:

- Univariate analysis of individual predictors, and subsequent construction of multivariate logistic regression models incorporating all significant univariate predictors.
- Parsimonious multivariate logistic regression models constructed through stepwise selection algorithm.
- Classification and regression tree models.

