**Table 6: Investigator Reporting Requirements**

Event Classification	Communication Method	Communication Timeline
Unanticipated Serious Adverse Device Effect	Complete AE eCRF page with all available new and updated information	
 
○ Within 1 business day of first becoming aware of the event.
 
○ Terminating at the end of the study
 

Serious Adverse Event including Serious Adverse Device Effects	Complete AE eCRF page with all available new and updated information	
 
○ Within 2 business days of first becoming aware of the event or as per local/regional regulations.
 
○ Reporting required through the end of the study
 

	Provide all relevant source documentation (unidentified) for reported event	
 
○ When documentation is available
 

Adverse Event	Complete AE eCRF page, which contains such information as date of AE, treatment of AE resolution, assessment of seriousness and relationship to the device	
 
○ No later than 14 working days after becoming aware of the information
 
○ Reporting required through the last visit of the patient in the study, with the exception of following up open adverse events until resolved or considered stable.
 

Device Deficiencies (including but not limited to failures, malfunctions, and product nonconformities) Note: Any Investigational Device Deficiency that might have led to a serious adverse event if a) suitable action had not been taken or b) intervention had not been made or c) if circumstances had been	Complete applicable Device Deficiency CRF page with all available new and updated information	
 
○ Investigators should report within 14 business days of first becoming aware of the event and as per local/regional regulations
 
○ Reporting required through the end of the study
 

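### Section 10.2 stops data collection after any withdrawal, even where consent stands, and requires no vital-status check beyond contacting the subject, so 2-year death and stroke rates may be understated if loss is linked to outcome

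*Combined protocol and SAP*

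**What the plan says.** Section 10.2 gives the reasons for withdrawal: "Reasons for withdrawal may include physician discretion, subject choice to retire consent, loss to follow-up, or death". Later in the section it states: "Additional data may no longer be collected after the point at which a subject has been withdrawn from the study". That sentence goes on to name withdrawal of consent as an alternative trigger and applies the rule regardless of the reason. It makes no exception for vital status.

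On tracing, Section 10.2 asks for significant effort before a subject is called lost, and specifies: "At a minimum there should be 3 documented telephone contact attempts and one certified letter sent to the subject's last known residence". It names no relative, treating physician, hospital record or death register.

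Two places point the other way. When a subject decides to withdraw, Section 10.2 says "every effort should be made to obtain full information on any on-going adverse events". Table 6 ends adverse event reporting at the last visit, "with the exception of following up open adverse events until resolved or considered stable". Data already collected are kept: "Data collected up to the point of subject withdrawal may be used", unless local rules require removal.

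For time-to-event analyses, Section 12.2 says "all subjects not having an event or lost to follow-up will be censored at the time of the last documented follow-up visit". It plans no sensitivity analysis for loss. Section 7 lists, among the primary analyses, "procedural complications, incidence of stroke and death".

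**The concern.** A stop on data collection is needed when a subject revokes consent. It is not needed when a physician withdraws the subject, or when contact is lost while consent stands. In those cases the rule can shut out a death or stroke that the site learns of afterwards.

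The required search goes to the subject's own telephone and address. After the visit at 1-3 months, scheduled contact is annual and may be by telephone (Sections 11.1 and 11.6). The site's first sign of a death or disabling stroke may therefore be an unanswered call. Such a subject can meet the definition of lost and be censored at a visit before the event.

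Censoring of this kind is harmless only if loss is unrelated to outcome. The registry has no comparator and no hypothesis test, so the absolute rates are its result, and Section 6 says the data may be needed for reimbursement. If lost subjects fare worse, the error runs in one direction, and a larger sample does not remove it.

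**Working it through.** **Inputs from the documents.** Up to 1000 subjects, an assumed event rate of 5% and a two-sided 95% interval (Section 12.1, Table 3); two years of follow-up (Section 11.7).

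**Assumptions, because the documents give no figures.** 5%, 10% or 15% of subjects lost over two years; a death hazard after loss that is k = 1, 2 or 3 times the hazard before loss; 2-year mortality m of 5% or 10% at the hazard seen under follow-up.

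**Step 1: the plan's precision.** Half-width = 1.96 × √(p(1−p)/n). At p = 5% this gives 1.91, 1.56 and 1.35 points for n = 500, 750 and 1000, which match the 1.9, 1.6 and 1.4 in Table 3. At p = 10% and n = 1000 it is 1.96 × √(0.10 × 0.90/1000) = 1.86 points. These figures cover sampling error only and use the full n.

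**Step 2: effect of unrecorded deaths.** Take exponential times to death and to loss, with censoring at the moment of loss.

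- Death hazard under follow-up: h = −ln(1−m)/2, which is 0.0256 per year at m = 5%.
- Loss hazard c is chosen so that c/(c+h) × (1−exp(−2(c+h))) equals the fraction lost.
- Recorded deaths as a crude proportion: h/(c+h) × (1−exp(−2(c+h))).
- Deaths after loss: the integral from 0 to 2 of c·exp(−(c+h)t) × [1−exp(−kh(2−t))] dt.
- True mortality is recorded deaths plus deaths after loss. The Kaplan-Meier estimate returns m.

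Example with m = 5%, 10% lost and k = 2: c is about 0.054, recorded deaths are 4.74% and true mortality is 5.25%. Kaplan-Meier is low by 5.25 − 5.00 = 0.25 points. The crude proportion is low by 5.25 − 4.74 = 0.51 points.

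Understatement in percentage points, Kaplan-Meier / crude proportion:

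| m | Lost | k = 1 | k = 2 | k = 3 |
|---|---|---|---|---|
| 5% | 5% | 0.00 / 0.13 | 0.12 / 0.25 | 0.24 / 0.37 |
| 5% | 10% | 0.00 / 0.26 | 0.25 / 0.51 | 0.49 / 0.75 |
| 5% | 15% | 0.00 / 0.39 | 0.38 / 0.77 | 0.74 / 1.14 |
| 10% | 5% | 0.00 / 0.26 | 0.24 / 0.50 | 0.47 / 0.73 |
| 10% | 10% | 0.00 / 0.53 | 0.49 / 1.02 | 0.95 / 1.47 |
| 10% | 15% | 0.00 / 0.80 | 0.74 / 1.54 | 1.44 / 2.23 |

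As a rough check, the Kaplan-Meier error is close to m × fraction lost × (k−1)/2, because loss falls on average about midway through follow-up: 5% × 0.15 × 2/2 = 0.75, against 0.74.

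**Step 3: a count that needs no hazard model.** In 1000 subjects, 13.5 unrecorded deaths shift a crude rate by 1.35 points, the half-width at 5%. That requires 13.5/50 = 27% of 50 lost subjects to have died, 13.5/100 = 13.5% of 100, or 13.5/150 = 9% of 150.

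**Step 4: the wording.** The stop in Section 10.2 admits no further data once a subject is withdrawn. The same section asks for full information on ongoing events, and Table 6 follows open events until they resolve or are stable. A site cannot tell from these three statements whether the outcome of an open event, including death, may be entered after withdrawal.

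**The case against.** The text is less restrictive than it may look, and four stronger readings go too far.

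- A reader might infer that sites may search only through the subject's telephone and address. The calls and letter are a stated minimum within a duty of significant effort. Section 11.8 names hospital records as source documents, and Section 16.2 has the investigator inform the subject's personal physician, with approval or where national rules require it. Wider tracing is not required, but it is not forbidden before loss is declared.
- A reader might infer that all later data are excluded. The open-event wording in Section 10.2 and Table 6 contradicts that.
- A reader might infer that the stop certainly covers lost subjects. Section 10.2 lists loss as a reason for withdrawal, which makes this the natural reading. The same section also names withdrawal and loss as separate items on the end-of-study form, so it is not the only reading. For physician-initiated withdrawal there is no such doubt.
- A reader might infer that mortality is understated as a matter of fact. A death known to the site is itself a listed reason for withdrawal, and a stroke known to the site is a serious event reportable to the end of the study. Only events the site has not learned of before withdrawal or loss are exposed, and Kaplan-Meier is unbiased if loss is unrelated to outcome.

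It can also be said that a descriptive registry with an open-ended analysis list need not prespecify a sensitivity analysis. That carries some weight, but death and stroke are named primary analyses, and the censoring rule rests on an assumption the plan does not test. The consent text is not among the documents, so whether it already permits contact with relatives or physicians cannot be judged.

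**Conclusion.** The point stands as a risk created by a stated rule. Section 10.2 can discard later-known deaths and strokes in subjects who never revoked consent, it requires no vital-status check beyond contacting the subject, and Section 12.2 does not examine the consequence.

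Under the assumed 5-15% lost and a 2-3 times higher death hazard after loss, the Kaplan-Meier understatement is about 0.12-0.74 points at 5% mortality and 0.24-1.44 points at 10%. Each range lies below the matching half-width of 1.35 or 1.86, but this error adds to sampling error and runs one way. A crude proportion over all subjects is low even at k = 1, because deaths after loss go uncounted. At 10% mortality, 15% lost and k = 3, its shortfall of 2.23 points exceeds the half-width.

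A reader might multiply retained mortality by the fraction lost and by the excess ratio, for example 5% × 0.15 × 2 = 1.5 points. That compares full 2-year mortality in lost and retained subjects. Under the plan's censoring rule, time before loss still counts, so the figure is roughly halved.

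The calculation was run for death only. The same mechanism applies to stroke, but no size is claimed for it.

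**What to change.** **Section 10.2 and Table 6**

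- Limit the stop on further data to subjects who revoke consent, and state whether it applies to loss to follow-up.
- Reconcile the stop with the wording on ongoing and open adverse events in both places.
- Where consent stands, enter any death or stroke that becomes known to the site, with its date.
- Before declaring a subject lost, require a check of the site's own hospital records and, where consent and local law allow, of the treating physician, next of kin or a death record.

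**Section 12.2**

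- Report the share of subjects with known vital status at two years.
- Add a sensitivity analysis with higher event rates after loss, over a stated range such as the 2-3 times used above.

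**Cost.** A wording amendment and some site effort per lost subject: at the assumed 5-15%, this is 50-150 of 1000 subjects across up to 70 sites. Where the consent text must change, ethics review is needed, and under Section 19 the ethics committee decides who must re-consent. Some countries may not permit every source. No visit or procedure is added, so the observational design in Section 8.2 is unaffected.
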